2.9 Pharmacokinetic endpoints

Analysis of PK endpoints are included in primary and secondary analysis sections ([Section 2.5](#) and [Section 2.7](#)) as they are considered primary and secondary endpoints in this study.

2.10 PD and PK/PD analyses

The arithmetic and geometric mean of PK concentration at each time point will be calculated for each treatment group. Graphic presentation will also be provided by treatment group.

2.11 Patient-reported outcomes

Not applicable for this study.

2.14 Interim analysis

As this is an open-label study with primary objective of pharmacokinetic endpoints and no interim analyses on which statistical comparisons will be made is planned, there is no relevance on blinding or alpha-adjustment.

Periodic interim safety analyses to support regulatory updates and interim reports may be warranted.

An interim analysis will be conducted to assess the variability of data as measured by coefficient of variation (CV) when approximately 36 patients total randomized in the PFS (abdomen) and AI (abdomen) treatment groups have completed Week 12. The purpose of this interim analysis is to provide an opportunity to increase the sample size so that sufficient power for the bioequivalence testing can still be achieved in case the estimated CV is larger than the assumed value of 85% at design stage. If deemed necessary, the sample size for the bioequivalence testing can be increased from 120 to a maximum of 250 completed patients.

3 Sample size calculation

The grand total sample size of this study is estimated by sum of the estimated sample size in all 4 treatment groups.

Section 3.1 provides sample size calculation for groups 1 and 2, which are used to address our primary objective. This sample size may be increased by the results of the interim analysis.

Section 3.2 provides sample size calculation for groups 3 and 4. This sample size will not be impacted by the results of the interim analysis.

3.1 Sample size calculation for PFS (abdomen) and AI (abdomen)

A total of 120 patients (60 per arm) will be required to achieve 90% power in the testing of bioequivalence between these two groups assuming their geometric mean ratio (GMR) = 1 and the coefficient of variation (CV) = 85%, which are considered reasonable and conservative assumptions according to previous experience with the variability of drug concentration pharmacokinetic parameters. To account for 3% dropout, a total of 124 patients (62 per arm)

will be randomized. The dropout rate assumption is based on data observed in the on-going phase III studies.

Due to limited PK data in the existing databases, CV can't be assessed accurately. Therefore, an interim analysis is planned to re-assess the CV of C_{max} and AUC_{tau}. Details are as described in [Section 2.14](#). If deemed necessary, the sample size for the BE testing can be increased to a maximum of 250 (125 per arm), in which case, the total number of patients to be randomized will be 258 (129 per arm) accounting for 3% dropout. The maximum sample size will provide approximately 80% power if the true CV is as high as 240%.

The sample size calculation is based on simulation for the testing procedure via a mixed scaling approach as described in [Section 2.5.2](#). Specifically, for a given CV on the natural scale, which is assumed to be the same for the two groups, and an assumed value of the GMR, 10,000 parallel groups trials with a given total sample size n are simulated and the proportion of trials that lead to a decision to declare ABE are recorded. If this value of n does not give a power greater than or equal to 0.9 then the n is increased in steps of 2, until a power of 0.9 is first achieved or exceeded. This n is then taken as the sample size that gives 90% power for the chosen values of CV and GMR. The estimated sample sizes for a range of values of CV and three values assumed for the GMR are given in below table.

Total sample sizes to achieve 90% power for testing for RSABE in a two-group parallel groups design

(with $\sigma_0 = 0.25$ and $\theta = \left(\frac{\ln(1.25)}{\sigma_0}\right)$)

CV	GMR=0.95	GMR=1.00	GMR=1.05
0.30	84	66	82
0.35	78	66	78
0.40	74	66	74
0.45	72	66	72
0.50	74	66	72
0.55	76	68	76
0.60	82	72	82
0.65	92	80	90
0.70	102	88	100
0.75	114	98	112
0.80	126	108	126
0.85	138	120	136

As a comparison, the sample sizes required to achieve a power of 0.9, when the standard test (TOST) for ABE is used with a parallel groups design, are given in below table.

Total sample sizes to achieve 90% power for testing for standard ABE in a two-group parallel groups design with equivalence limits $(-\ln(1.25), \ln(1.25))$

CV	GMR=0.95	GMR=1.00	GMR=1.05
0.30	102	78	100
0.35	138	102	134
0.40	176	132	170
0.45	218	162	212
0.50	262	196	256
0.55	310	232	302
0.60	360	270	352
0.65	414	308	402
0.70	468	350	454
0.75	522	390	508
0.80	578	432	564
0.85	636	476	620

For true CV values larger than 0.30, the Type I error rate is controlled at true mean difference values equal to the FDA implied limits $[\pm (\log(1.25)/0.25) * \sigma]$ on the log-transformed scale (see [Draft Guidance on Bioequivalence, 2001], [Draft Guidance on Progesterone, 2011]), where $CV = \sqrt{e^{\sigma^2} - 1}$.

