6.2 Pharmacokinetics sampling

The primary objectives of this trial are depending upon the pharmacokinetics assessment of the study drug. Bioequivalence will be evaluated statistically based on AUC_{tau} and C_{max} values from individual patient time-concentration profiles of ofatumumab. Data from patients randomized to group 1 and 2 will be used for the bioequivalence assessment. Hence, it is of key importance that the dosing instructions, samples collection procedures and timing of visits during the study are followed closely. The dosing interval between Week 8 and Week 12 is of particular importance to obtaining accurately assessed bioequivalence data. Pharmacokinetics sampling has been scheduled prior to dosing on all dosing visits. The time window in which the respective visits should occur, is also specified in the assessment schedule (see [Table 6-1](#)). If, for some reason, the visit cannot be completed within the specified time window, the planned dose administration and associated blood sampling should still be carried out as close as possible to the originally planning time points. In all cases, the PK sample collection date and time must be recorded as instructed in the lab manual and entered in the appropriate CRF.

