9.4.2 Statistical model, hypothesis, and method of analysis

To address the primary objective of testing bioequivalence at dosing interval after Week 8 between PFS and AI, the primary analysis involves the two groups (PFS (abdomen) and AI (abdomen)). In the following, the PFS (abdomen) group will be referred to as the Reference (or R) group and the AI (abdomen) group as the Test group (or T).

The null hypothesis is that “Mean difference in \ln (AUCtau) and/or \ln (Cmax) greater than allowed-difference between these 2 groups” ($H_0: |\mu_T - \mu_R| > \Delta$). The alternative hypothesis is that “Mean difference in \ln (AUCtau) and \ln (Cmax) less than allowed-difference between these 2 groups” ($H_a: |\mu_T - \mu_R| \leq \Delta$). \ln refers to the natural log function. The testing procedure is described below.

As the testing for Average Bioequivalence (ABE) will be based on a between-groups comparison, the variabilities of the R and T groups are expected to be high, with a coefficient of variation (CV) greater than 0.3. Hence, the FDA recommended, Reference-scaled average bioequivalence (RSABE) bioequivalence approach for highly variable drugs is proposed.

As there is no FDA guidance for using RSABE in a parallel groups design, the current guidance for cross-over trials ([Davit et al, 2012](#), [Draft Guidance on Progesterone, 2011](#),) has been modified for application in a parallel groups design.

The between-subject variability for the R group will take the place of the within-subject variability for R.

[REDACTED]

A mixed scaling approach will be used: (1) if the standard deviation of the R group data (on the log scale) exceeds 0.294, the traditional ABE limits of $\ln(0.8)$ and $\ln(1.25)$ will be scaled by the between-subject variability for the R group, (2) otherwise the standard TOST (two one-sided test) approach for (unscaled) ABE will be used. The regulatory constant used in the linearised criterion for the RSABE approach will be set to $\sigma_0 = 0.25$ (as in the recommended RSABE approach for cross-over trials).

The steps in the analysis will therefore be:

1. Calculate s_R the standard deviation of the R group subjects' data on the log-scale (for AUCtau or Cmax).
2. If $s_R < 0.294$ then apply the standard ABE criteria, ie, determine if the 90% confidence interval for the mean difference between T and R on the log-scale, $(\mu_T - \mu_R)$, lies within $[-\ln(1.25), \ln(1.25)]$.

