9.8.1 Sample size calculation for PFS (abdomen) and AI (abdomen)

A total of 120 patients (60 per arm) will be required to achieve 90% power in the testing of bioequivalence between these two groups assuming their geometric mean ratio (GMR) = 1 and the coefficient of variation (CV) = 85%, which are considered reasonable and conservative assumptions according to previous experience with the variability of drug concentration pharmacokinetic parameters. To account for 3% dropout, a total of 124 patients (62 per arm) will be randomized. The dropout rate assumption is based on data observed in the on-going Phase III studies.

Due to limited PK data in the existing databases, CV can't be assessed accurately. Therefore, an interim analysis is planned to re-assess the CV of Cmax and AUCtau. Details are as described in [Section 9.7](#). If deemed necessary, the sample size for the BE testing can be increased to a maximum of 250 (125 per arm), in which case, the total number of patients to be randomized will be 258 (129 per arm) accounting for 3% dropout. The maximum sample size will provide approximately 80% power if the true CV is as high as 240%.

The sample size calculation is based on simulation for the testing procedure via a mixed scaling approach as described in [Section 9.4.2](#). Specifically, for a given CV on the natural scale, which is assumed to be the same for the two groups, and an assumed value of the GMR, 10,000 parallel groups trials with a given total sample size n are simulated and the proportion of trials that lead to a decision to declare ABE are recorded. If this value of n does not give a power greater than or equal to 0.9 then the n is increased in steps of 2, until a power of 0.9 is first achieved or exceeded. This n is then taken as the sample size that gives 90% power for the chosen values of CV and GMR. The estimated sample sizes for a range of values of CV and three values assumed for the GMR are given in below table.

Total sample sizes to achieve 90% power for testing for RSABE in a two-group parallel groups design

(with $\sigma_0 = 0.25$ and $\theta = \left(\frac{\ln(1.25)}{\sigma_0} \right)$)

CV	GMR=0.95	GMR=1.00	GMR=1.05
0.30	84	66	82
0.35	78	66	78
0.40	74	66	74
0.45	72	66	72
0.50	74	66	72
0.55	76	68	76
0.60	82	72	82
0.65	92	80	90
0.70	102	88	100
0.75	114	98	112
0.80	126	108	126
0.85	138	120	136

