3. If $s_R \geq 0.294$ then apply the reference scaled ABE criteria, i.e., determine if, $-\theta_s \leq \frac{(\mu_T - \mu_R)}{s_R} \leq \theta_s$ where $\theta_s = \frac{\ln(1.25)}{\sigma_0}$, and $\sigma_0 = 0.25$. This is done by calculating an approximate 95% upper confidence bound for the linearised criterion, $(\mu_T - \mu_R)^2 - \theta_s^2 \sigma_R^2$. If this upper bound is less than or equal to zero and the point estimate of the T/R geometric mean ratio (GMR) falls within (0.8, 1.25), then ABE is declared (i.e., the null hypothesis is rejected).

Testing will be performed as above for AUCtau and Cmax separately on the BE analysis set.

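### The stated 90% and approximately 80% powers are for one PK parameter, but the primary claim needs AUCtau and Cmax both to pass, and joint power is not given

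*SAP*

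**What the plan says.** SAP 3.1, with the same text in Protocol 9.8.1, sizes the two abdomen groups: "A total of 120 patients (60 per arm) will be required to achieve 90% power in the testing of bioequivalence between these two groups". The assumptions are GMR 1 and CV 85%, "which are considered reasonable and conservative assumptions". For the largest size the interim analysis can lead to (250 completers), Protocol 9.8.1 says: "The maximum sample size will provide approximately 80% power if the true CV is as high as 240" per cent.

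The powers come from simulation. It runs "for a given CV on the natural scale, which is assumed to be the same for the two groups", with one assumed GMR, and "the proportion of trials that lead to a decision to declare ABE are recorded". No second parameter and no correlation appear.

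On the hypotheses, Protocol 9.4.2 and SAP 2.5.2 agree. The null is a difference beyond the limit in either or both parameters. The alternative is "Mean difference in \ln (AUCtau) and \ln (Cmax) less than allowed-difference between these 2 groups". On execution, SAP 2.5.2 says: "Testing will be performed as above for AUCtau and Cmax separately on the BE analysis set".

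**The concern.** With an either-or-both null, bioequivalence is concluded only if both tests succeed. Running the tests separately describes how each is done; it does not make one of them sufficient. The probability of success is therefore the probability that both parameters pass in the same trial. That is below the power for either one unless the two decisions always coincide or the other parameter almost never fails.

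The quoted powers are worded as power for the bioequivalence test and placed under the primary objective, without a per-parameter label. A reader will take 90%, or 80% at the maximum size, as the chance that the trial meets its primary objective.

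A related wording problem concerns GMR 1. It is the most favourable value tabulated: at CV 0.85 the plan's reference-scaled table needs 120 completers at GMR 1.00, against 138 at 0.95 and 136 at 1.05. The table gives the sample sizes needed away from GMR 1, but not the power of the chosen 120.

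**Working it through.** **Inputs from the documents.** 60 or 125 completers per arm; CV 85% or 240%; GMR 1; switch to scaling at s_R = 0.294; σ0 = 0.25; 95% upper bound on the linearised criterion; point estimate of the GMR within 0.8 to 1.25.

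**Inputs not in the documents (assumed).** The correlation ρ between ln AUCtau and ln Cmax, and a separate CV for each. A high ρ is plausible because both are "values from individual patient time-concentration profiles of ofatumumab" (Protocol 6.2). ρ = 0 is shown only as a lower bound.

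**Step 1: reproduce the plan's figures for one parameter.** The log-scale SD is σ = √ln(1 + CV²). The standard error of the mean difference, with m per arm, is SE = σ√(2/m). At these CVs the scaled limit is wide: (ln 1.25/0.25)σ = 0.893 × 0.737 = 0.66 at CV 85%, against ln 1.25 = 0.223. The point-estimate limit therefore governs, and at GMR 1 power ≈ 2Φ(0.223/SE) − 1.

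- 120 completers, CV 85%: σ = √ln(1.7225) = 0.737; SE = 0.737 × √(2/60) = 0.1346; 0.2231/0.1346 = 1.657; power = 0.903.
- 250 completers, CV 240%: σ = √ln(6.76) = 1.382; SE = 1.382 × √(2/125) = 0.1749; 0.2231/0.1749 = 1.276; power = 0.798.

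Simulating the full mixed procedure (40,000 trials, Howe-type upper bound) gives 0.903 and 0.800. It gives 0.8998 at 118 completers and 0.903 at 120, so 120 is the single-parameter answer. Other table cells agree: CV 0.70, n = 88 gives 0.90; CV 0.85, GMR 0.95, n = 138 gives 0.90. Dropout inflation to 124 and 258 is also right.

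**Step 2: joint power.** This is the probability that both estimated log differences lie within ±ln 1.25, from a bivariate normal with correlation ρ and the standard errors above. At ρ = 0 and equal CVs it is the square: 0.903² = 0.815 and 0.798² = 0.637.

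| Completers | CVs of the two parameters | GMR | Single (larger CV) | ρ = 0 | 0.8 | 0.9 | 0.95 |
|---|---|---|---|---|---|---|---|
| 120 | 85%, 85% | 1 | 0.903 | 0.815 | 0.853 | 0.867 | 0.877 |
| 120 | 85%, 75% | 1 | 0.903 | 0.842 | 0.873 | 0.885 | 0.893 |
| 120 | 85%, 70% | 1 | 0.903 | 0.855 | 0.882 | 0.891 | 0.897 |
| 120 | 85%, 65% | 1 | 0.903 | 0.867 | 0.889 | 0.896 | 0.900 |
| 120 | 85%, 85% | 0.95 | 0.878 | 0.772 | 0.822 | 0.838 | 0.850 |
| 120 | 85%, 85% | 1.05 | 0.881 | 0.776 | 0.825 | 0.841 | 0.853 |
| 250 | 240%, 240% | 1 | 0.798 | 0.637 | 0.710 | 0.735 | 0.754 |
| 250 | 240%, 200% | 1 | 0.798 | 0.667 | 0.734 | 0.757 | 0.773 |
| 250 | 240%, 150% | 1 | 0.798 | 0.715 | 0.767 | 0.783 | 0.792 |

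Full simulation of the equal-CV, GMR 1 rows agrees: 0.856, 0.869 and 0.878 at 120 completers, and 0.711, 0.735 and 0.754 at 250, for ρ = 0.8, 0.9 and 0.95. Even at ρ = 0.99 it gives 0.888 and 0.779.

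**Step 3: what would make the 90% true.** With a common CV and GMR 1, 120 completers give 90% joint power only if that CV is at most about 69%, 74%, 77% or 79% for ρ = 0, 0.8, 0.9 or 0.95.

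**The case against.** The best defence is that nothing is miscalculated. Every stated figure reproduces. The sample-size text refers to the testing procedure, which is written per parameter and ends in a declaration for that parameter, so the simulated decision can be read as the per-parameter one. That stands, and it locates the fault in the label rather than the arithmetic. It does not remove the fault: the sample-size section presents the figure as power for the bioequivalence comparison that serves the primary objective.

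Second, the size of the shortfall depends on quantities the documents do not give. If both CVs were 75%, joint power at 120 completers would be 0.896, 0.907 and 0.914 at ρ = 0.8, 0.9 and 0.95; with CVs of 80% and 65% it would be 0.903, 0.910 and 0.914. The 240% case is worded as an extreme, and two parameters both at that extreme is the worst version of it. All true, which is why a range is needed and not one replacement figure.

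Third, the interim analysis re-assesses the CV of both parameters and can raise the sample size. That makes 90% provisional, but the interim section names no joint-power target and no correlation.

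Fourth, the basis offered for calling the assumptions conservative is experience with variability, which concerns CV, and the plan does tabulate sample sizes at GMR 0.95 and 1.05. This weakens the GMR point to one of wording: the sentence covers both assumptions, and the per-parameter loss at 120 completers is only about 2 points (0.903 to 0.878 or 0.881).

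**Conclusion.** The concern holds. The 90% and approximately 80% are correct for one parameter and are presented as power for a decision that needs two. With both parameters at the plan's single CV and GMR 1, joint power falls short of the stated value by about 2 to 5 points at 120 completers and 5 to 9 points at 250, for ρ between 0.95 and 0.8. In that setting the stated power is reached only at a correlation of nearly 1. With one CV held at 85%, the shortfall at 120 completers disappears only if the other is about 65% or less and ρ is about 0.95. It also disappears if both CVs are sufficiently below 85%.

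These sizes rest on an assumed correlation, assumed CVs and log-normal data. Requiring both tests to pass needs no alpha adjustment, so type I error, the test and the decision rule are untouched. What is affected is the stated chance of success.

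**What to change.** In SAP 3.1, and in the matching text of Protocol 9.8.1:

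1. Label the 90% and approximately 80% as power per parameter.
2. Add: *Bioequivalence requires AUCtau and Cmax both to pass. Joint power depends on their correlation and on the CV of each parameter, which are not known at the design stage.* Follow this with a small table of joint power over stated correlations and CVs, such as the one above, rerun with the sponsor's own simulation code.
3. Stop describing GMR 1 as conservative, and give the power of 120 completers at GMR 0.95 and 1.05: about 88% per parameter, and about 82-85% jointly at ρ = 0.8 to 0.95 with both CVs at 85%.

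The current SAP version is dated after database lock, so this corrects the description only. No change to sample size, interim sizing, analysis or decision rule is proposed. The cost is wording plus one simulation rerun. Changing the protocol text also needs a formal amendment under Protocol 11.1; if the protocol is not being reopened, SAP 3.1 can carry the clarification and say that it applies to Protocol 9.8.1 as well. The stated chance of success becomes somewhat less favourable.

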3.2 Sample size calculation for PFS (thigh) and AI (thigh)

Sample size requirement is based on a conventional size of studies for an evaluation of pharmacokinetic endpoints in treatment groups with different administration sites (i.e., comparing PFS (abdomen) vs. PFS (thigh) or comparing AI (abdomen) vs. AI (thigh)). No formal statistical testing is planned.

A total of 24 patients (12 per arm) will be required for PFS (thigh) and AI (thigh) groups. This is in alignment with sample size often applied to standard pharmacokinetic studies.

For an estimation of mean difference in the two groups of different administration sites (abdomen (n=60) vs. thigh (n=12)), the width of 90% CI will be 0.78 assuming the CV is 85%.

To account for 3% dropout, a total of 26 patients (13 per arm) will be randomized.

4 Change to protocol specified analyses

Plots of median instead of mean B-cell counts by treatment group against time point, for consistency with outputs for Phase III studies.

The current study protocol (version 00) stated the use of CTCAE version 4.03. As the latest CTCAE version 5 is available, Section 5.3.3 includes CTCAE grade definitions based on version 5.

5 Appendix

5.1 Imputation rules

5.1.1 Study drug

Missing or partial dates are not allowed in completing the study drug administration CRF pages. The end date of study drug will be the last injection date.

5.1.2 AE date imputation

For the start and end dates of the adverse event records, when incomplete or missing, dates will be imputed according to Novartis standards (details will be given in programming datasets specifications (PDS) document).

5.1.3 Concomitant medication date imputation

For the start and end dates of the concomitant medication records, when incomplete or missing, dates will be imputed according to Novartis standards (details will be given in programming datasets specifications (PDS) document).

5.1.3.1 Prior therapies date imputation

Same as above.

5.1.3.2 Post therapies date imputation

Same as above.

5.1.3.3 Other imputations

For the calculation of duration or time since relevant history events as specified in [Section 2.3.3](#) (MS disease baseline characteristics), partial dates will be imputed for the MS diagnosis start date, the first MS symptom date, the conversion to SPMS date, and the most recent relapse onset date via below imputation rules.

- If the year is missing or impossible (e.g. 12-Jan-1911), then the date will be imputed as missing.
- If the year is not missing and possible, but the month is impossible or missing (e.g. 17-XXX-2010), then the year will be kept and date will be imputed as July 1st (e.g., 1-July-2010).
- If the year and the month are not missing and possible, but the day is impossible or missing (e.g. 31-FEB-2009), then the year and month will be kept, and date will be imputed as 15th (e.g., 15-FEB-2009).

The imputed dates should be prior to the screening visit date. That is, if imputed dates are on or after the screening visit date, the dates will be imputed to be one day before the screening visit date.

5.2 AEs coding/grading

AEs are coded using the Medical dictionary for regulatory activities (MedDRA) terminology. The latest MedDRA version will be used and will be described in the footnote of relevant outputs.

AEs will be assessed according to the Common Terminology Criteria for Adverse Events (CTCAE).

The CTCAE represents a comprehensive grading system for reporting the acute and late effects of cancer treatments. CTCAE grading is by definition a 5-point scale generally corresponding to mild, moderate, severe, life threatening, and death. This grading system inherently places a value on the importance of an event, although there is not necessarily proportionality among grades (a grade 2 is not necessarily twice as bad as a grade 1). The CTCAE grade of 5 (death) is not used; rather, ‘fatal’ is collected as AE outcome and death information is also collected on a separate (e)CRF page.

